3.2 Participant assignment to clinics

Participating GUM clinics will be assigned recruitment targets which will be allocated to ensure inclusion for MSM and non-MSM participants. Recruitment will be monitored centrally.

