3.4 Number of participants

This trial aims to enrol 13,000 participants.

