5.9 Procedures for tracking patients across clinics

Patients often move between different sexual health services; we are anticipating that this could also occur within the context of this trial. Participants can be tracked across different clinics using their trial ID, which is assigned upon trial enrolment, but will not be able to be tracked via their GUMCAD number. GUMCAD numbers are allocated per patient and per clinic and therefore cannot be transferred across different services. In order to mitigate the risk of a participant enrolling twice, and hence taking two

places on the trial and affecting statistical analysis, patients will be asked to disclose that they are already on the trial if they move to a different clinic. This is stated in the participant information sheet and places importance of not double-enrolling on the trial from the perspective of denying another person access to PrEP. The participant's trial ID will be clearly documented on their copy of the completed informed consent form, which needs to be provided and verified when transferring to another clinic.

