6.2 Provision of treatment after the end of the trial

As the trial is non-interventional, post trial access to PrEP cannot be guaranteed to participants. PrEP is licensed for use in the UK and available to purchase privately, however it is currently unavailable on the NHS in England. All data generated from the trial will be presented to the TSC and provided to commissioners via the Oversight Board to inform future commissioning decisions on PrEP. The Board will seek to review the result of the research during the research period to minimise any gap in future commissioning and implementation decisions being taken. It is expected that the trial data will inform the commissioning of a PrEP programme to be implemented promptly on conclusion of the trial. Information will be shared with NHS England as commissioners of HIV drugs and local authorities as commissioners of sexual health services. It is anticipated that a national programme will be put in place with the expectation that PrEP will be available to all who are eligible, as informed by the data from this trial.

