8 STATISTICAL CONSIDERATIONS AND DATA MANAGEMENT

8.1 Sample Size

The trial will recruit from the 'total' GUM clinic attending population in participating trial clinics. This is a subset of the 'total' GUM clinic attending population. A proportion of the attendees in participating GUM clinics will meet the trial eligibility criteria and of these the trial will recruit a total of 13,000 participants to receive PrEP. Estimates from GUMCAD 2016 suggested that the total eligible MSM population across all GUM clinics was approximately 10,000. The 10,000 target was considered sufficient to allow the size of the total eligible population (MSM and women and others) across all GUM clinics to be estimated with a precision within the range ± 480 to ± 1150 . These precision estimates were derived from a range of simulations using a number of assumptions derived from available GUMCAD data at the time. These include: the proportion of MSM meeting the eligibility criteria (estimated range 20% to 60%), the percentage of MSM at high risk (percentage with a bacterial STI in past year 25% to 55%), and percentage of non-MSM eligible (20% of the eligible MSM population).

Before the trial began and assuming that PrEP uptake in the eligible population lay within the range 20% to 60%, a trial size of 10,000 participants was deemed to be sufficient to estimate the precision for PrEP uptake within $\pm 3\%$.

Co-variables of major interest include clinic, clinical history of genital and rectal bacterial STI, geographical area of the country, age, and ethnicity. The possible combinations of these co-variables results in potential for large standard errors when considering sub group analysis.

Therefore, assuming that the smallest critical sub-group represents 5% of the trial population, the sample size of 10,000 provides a sufficiently narrow precision within each sub-group of 500 participants about the estimated numbers of eligible attendees (± 44 to ± 64) and the precision around the estimated proportion taking up the offer of PrEP of $\pm 6\%$.

The distribution, and the average duration of PrEP use are dependent upon the risk spectrum of the eligible population, and their duration of eligibility.

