Based on the cumulative accrual of over 7,000 in the first 8 months of opening, mainly MSM, the Trial Management Group and independent Steering Committee, supported by the NIHR, have advised NHS England and the Association of the Directors of Public Health (ADsPH) that increasing the original sample size of 10,000 to 13,000 would provide useful additional data and address concerns about the representativeness of those who were recruited to the trial over the initial few months. A trial with 13,000 participants should be sufficient to enable the detection of meaningful differences in duration between sub-groups of participants. However, both the mean and variance of the duration of PrEP use is currently unknown. If there is substantial variance in the duration distribution then excessive differences may fail to be detected in small sub-groups.

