8.3 Statistical Analysis

All analyses will be performed using STATA data analysis and statistical software version 13 or higher. Preliminary data review, analysis and presentation may be conducted throughout study duration at the request of the Trial Steering Committee. A detailed description of the analyses to be performed is outlined in the Statistical Analysis Plan (SAP). The analysis will address all outcomes of the trial and a descriptive baseline analysis will also be performed. Safety data will be extracted from 'yellow card' submissions.

To address the trial objectives, the following analyses will be undertaken:

- 1) PrEP eligibility: the total eligible population (numerator) will be estimated from the 'total' GUM attending clinic population (denominator). The clinic attending population will be categorised as 'eligible' or 'non-eligible' in participating clinics. Therefore, to estimate numbers eligible for PrEP among the 'total' GUM clinic attending population, a finite population correction will be used based on the total number of GUM clinics with post-hoc stratification weighting as necessary to account for observed differences between the sample and population with respect to important patient characteristics such as sexual orientation and age group.
- 2) Uptake of PrEP: The numerator is the population taking up an offer of PrEP, and denominator is the eligible population in participating GUM clinics. The uptake of PrEP will be estimated using a binomial generalised linear model with logarithmic link function, taking into account heterogeneity of clinics. An analysis of the predictors of PrEP uptake will be made, and will include time as a variable. There is a dynamic aspect to PrEP uptake (e.g. starting, stopping, restarting) which will be taken into consideration.
- 3) Duration of PrEP eligibility and use: Participants in the trial can be in one of three states: 'eligible for PrEP and on PrEP', 'eligible for PrEP but not on PrEP', and 'currently ineligible for PrEP'. Participants will move between these states. The analysis will use a multi-state model to estimate the

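### Once the 13,000 places fill, uptake over all eligible attendees mixes lack of places with unwillingness, and section 8.3 has no rule to separate them

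*Combined protocol and SAP*

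**What the plan says.** Section 8.3, item 2, defines uptake: "The numerator is the population taking up an offer of PrEP, and denominator is the eligible population in participating GUM clinics". The model is a binomial GLM with log link that allows for clinic heterogeneity, includes time among the predictors, and is to take account of starting, stopping and restarting.

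Supply is described elsewhere in the protocol:

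- Section 3.4: "This trial aims to enrol 13,000 participants". Section 8.1 records that this was raised from 10,000.
- Section 3.2: "Participating GUM clinics will be assigned recruitment targets which will be allocated to ensure inclusion for MSM and non-MSM participants".
- Section 5.9 treats places as scarce. The participant information sheet "places importance of not double-enrolling on the trial from the perspective of denying another person access to PrEP".
- Section 6.2 says of PrEP that "it is currently unavailable on the NHS in England", although it can be bought privately.
- Section 3.1 has sites screen for eligibility at every new episode of care, so people are still classed as eligible after places have gone.

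On demand, section 8.1 says: "Estimates from GUMCAD 2016 suggested that the total eligible MSM population across all GUM clinics was approximately 10,000". It adds non-MSM at 20% of that number, assumes uptake of 20% to 60%, and claims precision of ±3% for uptake. It also reports: "Based on the cumulative accrual of over 7,000 in the first 8 months of opening, mainly MSM".

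Sections 8.5 and 8.6 say that GUMCAD captures eligibility, offer, outcome of the offer and uptake at participant level.

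**The concern.** The numerator needs an offer that was accepted. The denominator needs only eligibility. While places are open, the gap between them consists of people not offered PrEP and people who declined it, and both are real losses along the care continuum. Once places are gone, a third group enters: eligible people for whom no place exists. Section 8.3 does not distinguish this group, and the two biases it names (risk spectrum and health-seeking behaviour) do not cover it.

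Uptake is part of the trial's aim, objective 1 and outcome 1. Section 6.2 expects the results to inform a programme open to everyone eligible, that is, one without a limit on places. A ratio partly set by the number of places would understate what such a programme has to supply. Because time is a predictor, the filling of places could be read as falling demand. Clinic and MSM/non-MSM contrasts are exposed in the same way wherever a recruitment target actually stops enrolment.

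**Working it through.** **1. The plan's own precision.** The simple binomial 95% half-width is 1.96 × √(p(1−p)/n). With n = 10,000 it is ±0.78 points at p = 0.2, ±0.98 at p = 0.5 and ±0.96 at p = 0.6. The stated ±3 points would need a design effect of (3/0.98)² ≈ 9.4 at p = 0.5, rising to 14.6 at p = 0.2. The clustering inputs are not given, so the figure can be neither reproduced nor called wrong. It serves here only as a yardstick.

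**2. Planning figures.** Eligible: 10,000 × 1.2 = 12,000. Takers: 0.20 × 12,000 = 2,400 to 0.60 × 12,000 = 7,200. Both are below 13,000, so the limit does not bind.

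**3. General bound.** With E people cumulatively eligible and true uptake p, the defined ratio is min(p, 13,000/E). The limit binds when E > 13,000/p:
- p = 0.60: E above 21,667
- p = 0.20: E above 65,000

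**4. What accrual implies.** At least 7,000 / 8 = 875 per month. At 60% uptake, 7,000 takers already need 7,000 / 0.60 ≈ 11,667 eligible people, almost the whole planning total for all GUM clinics. At 20% they need 35,000.

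**5. When the limit stays slack.** Places left after month 8: 13,000 − 7,000 = 6,000. Months of recruitment left: 33 − 8 = 25. The sustainable pace is 6,000 / 25 = 240 per month, and 240 / 875 = 27% of the observed pace. As accrual was over 7,000, these are upper limits.

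**6. Illustrations.** Assumptions, not in the protocol: true uptake 60%, and new eligible people arriving in proportion to the enrolment there would be without a limit.

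| Pace after month 8 | Places gone at month | Would-be takers by month 33 | Share with a place | Implied eligible | A true 60% reads |
|---|---|---|---|---|---|
| 875 (unchanged) | 13,000/875 = 14.9 | 33 × 875 = 28,875 | 45% | 28,875/0.60 = 48,125 | 0.60 × 0.45 = 27% |
| 437.5 (halved) | 8 + 6,000/437.5 = 21.7 | 7,000 + 25 × 437.5 ≈ 17,938 | 72% | 17,938/0.60 ≈ 29,900 | 13,000/29,900 ≈ 43% |
| 240 or less | not before 33 | at most 13,000 | 100% | at most 21,667 | 60% |

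Where the limit binds, the shortfall is 33 points in the first row and about 17 in the second, against the stated ±3. In both rows uptake is 60% for people who become eligible before closure and zero, by construction, for those who become eligible after it. That step is what the time term would pick up.

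**The case against.** Several points on the other side are sound.

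- **Early pace may not last.** Section 8.1 itself raises the representativeness of the first recruits. Section 5.4.1 provides for people already on PrEP, and section 5.1 expects self-referral after media coverage, so an opening backlog is plausible. The month-15 date is an extrapolation.
- **The illustrations need many eligible people.** About 48,000 is four times the planning figure. A reader might apply the same 45% factor at the low end and infer that a true 20% would be reported as 9%. That needs 28,875 / 0.20 = 144,375 eligible people, twelve times the planning figure, and 20% is undistorted up to 65,000. The documents do not support it.
- **Hard quotas are not stated.** Section 3.2 speaks of targets with central monitoring. Nothing says that a clinic closes to a population on reaching its target, and the overall number has been raised once. That clinic or MSM/non-MSM contrasts will reflect quotas is therefore only a possibility.
- **Takers over all eligible is a legitimate continuum quantity.** It counts people who were never offered PrEP as a loss, which an offer-only ratio would hide. It should be kept, but not read as willingness.
- **People are not attendances.** Someone enrolled early who re-attends after closure is still a taker. Months without places become non-uptake only through newly eligible people.
- **A separate SAP exists.** Section 8.3 defers detail to a plan whose text is not in the document. It may address this, but section 8.3 already fixes the denominator and the two must agree.

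These points limit the size and certainty of the bias. None supplies a rule for eligible people without a place.

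**Conclusion.** The definition is valid until places fill. After that it is bounded by places/eligible and mixes capacity with willingness. Whether this happens depends on accrual after month 8: no bias if it stays at or below about 240 per month, and otherwise a shortfall that could be many times the stated precision. The 27% and 43% readings for a true 60% are illustrations that rest on the stated inflow assumption; they are not predictions.

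A reader might go further and conclude that the headline figure will measure the number of places instead of demand, or that the yearly proportion prescribed PrEP becomes uninterpretable. The documents do not support either as a certainty. The planning figures leave the limit slack, the period before closure is informative, and the coded offer data allow the two components to be separated.

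**What to change.** Amend section 8.3, item 2, and the SAP to match:

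1. Report two ratios from the GUMCAD offer codes: offered/eligible and accepted/offered. Use accepted/offered as the measure of willingness. Their product is accepted/eligible, so the continuum quantity is retained.
2. Count eligible attendees for whom no place was available separately from those who declined, and do not code them as offered. If the existing offer-outcome codes have no such value, add one.
3. Label the all-eligible ratio as coverage under capped supply, and state that its time trend is not to be read as demand.
4. As a supporting analysis, refit the uptake and time models on person-time before places closed, overall or by clinic and population where closure occurred.

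The cost is mainly wording, since offer and outcome are already coded. Closure dates must be recorded: section 3.1 requires monthly recruitment figures but does not say that they are split by population or show whether places are open. The restricted analysis gives more weight to early recruits, whose representativeness section 8.1 questions, and drops time from the clinics that fill fastest. For that reason it should support the main analysis and not replace it. The rule should be set before analysis, because declined and no place available may be impossible to tell apart afterwards.

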3.3 Inclusion and Exclusion Criteria

Inclusion Criteria

The participant populations for this trial will be men and women attending GUM clinics who belong to one of three populations recognised to be at high risk for HIV, namely:

A. Men (cisgender and transgender) and transgender women who:

1. Have sex with men
2. Have had an HIV negative test during an earlier episode of care in the preceding year
3. Report condomless intercourse (excluding oral) in the previous 3 months
4. Affirm their likelihood of having condomless (excluding oral) intercourse in the next 3 months

B. HIV negative partners of an HIV positive person when:

1. The HIV positive partner is not known to be virally suppressed (<200 copies/ml for 6 months or more)
2. Condomless intercourse (excluding oral) is anticipated before treatment of the HIV positive partner takes effect

C. HIV negative persons who:

1. Are clinically assessed and considered to be at similar high risk of HIV acquisition as those with a serodiscordant partner who is not known to be virally suppressed

Participants will therefore be considered eligible for trial enrolment if they fulfil all the following individual eligibility criteria:

- 1) Belong to one of the three at high HIV risk populations described above
- 2) Aged 16 years or over (no upper limit)
- 3) Considered to be HIV negative on the day of enrolment
- 4) Willing and able to provide informed consent
- 5) Willing to adhere to the recommended PrEP regimen
- 6) Willing to re-attend the trial clinic at appropriate intervals for risk assessment

Exclusion Criteria

Participants will not be considered eligible for trial enrolment if they fulfil any of the following criteria:

- 1) An acute viral illness that could be due to HIV seroconversion
- 2) Any contraindication to Tenofovir Disoproxil (TD)/ Emtricitabine (FTC) - according to the current package insert or SmPC

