4.4 PrEP discontinuation

Participants should stop PrEP in the event of any of the following reasons:

1. HIV infection;
2. Unacceptable toxicity or adverse event;

Participants may stop PrEP for any of the following reasons:

1. Any change in the participant's sexual behaviour or circumstances that justifies the discontinuation of PrEP;
2. On the recommendation of the Trial Steering Committee or termination of the trial by the sponsor or funder;
3. Participants may withdraw at any time and for any reason. They may withdraw without giving a reason but if one is given then this should be documented in the patient records;
4. Participants may be withdrawn at the discretion of the investigator, in the best interest of the participant.

Participants who are identified as HIV positive during baseline assessment or trial follow up will be managed according to local policies for linkage to HIV care.

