5.4.2 Early Follow-up in New Starters

For participants who have not taken PrEP or PEP previously, it is good practice to check how the participant is getting on. This can be done by phone email or in person if a visit is indicated for other reasons.

5.4.3 3-monthly Follow-up

In line with established practice, 3-monthly follow up is advised. Standard assessments and procedures at this time should be done in accordance with established clinical practice based on clinical evidence and include:

- A 4th generation HIV test,
- STI screen for chlamydia, gonorrhoea and syphilis according to established practice supported by clinical evidence or if clinically indicated,
- Hepatitis C testing according to established practice supported by clinical evidence,
- Urinalysis and serum creatinine or urinary protein/creatinine ratio if indicated
- Pregnancy testing if indicated clinically (see section 5.6),
- Prescribing and dispensing of drug according to agreed local practice (see section 5.5),
- Completion of GUMCAD codes,
- MHRA Yellow card reporting if appropriate.

The clinician should check that the participant is still eligible for PrEP and wishes to continue, and should record this information using the GUMCAD codes. Once standard assessments have

been undertaken, study drug can be prescribed and dispensed. A record of dispensing should be made in the study drug log/eCRF.

Participants should be offered relevant interventions from active risk reduction services as per the First Prescription visit (Section 5.4.1).

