8.2 Trial Outcomes

1. Proportion of Genitourinary Medicine (GUM) clinic attendees that meet PrEP eligibility criteria, the proportion that is prescribed PrEP per year and the duration of PrEP-eligibility and PrEP-use among users.

2. HIV and STIs:
 - a. HIV diagnoses in national dataset
 - b. STI diagnoses (gonorrhoea, chlamydia, syphilis and Hepatitis C) in national dataset
3. Adverse Events
 - a. Serious suspected adverse drug reactions reported using the yellow card system
 - b. Antiretroviral resistance associated mutations in participants with incident HIV infection

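### The three-state duration model merges ineligible participants on and off PrEP, so any PrEP time while ineligible is left out of duration of use

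*Combined protocol and SAP*

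**What the plan says.** **The model.** Section 8.3 item 3 says that "Participants in the trial can be in one of three states", namely "eligible for PrEP and on PrEP', 'eligible for PrEP but not on PrEP', and 'currently ineligible for PrEP". The multi-state model is to estimate the probability of each state, the proportion in each, the average time spent in each, and the transitions. Subjects may leave and re-enter the analysis according to their eligibility.

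**What it must deliver.** Outcome 1 in section 8.2 includes "the duration of PrEP-eligibility and PrEP-use among users". Objective 1 in section 2 also lists the two durations separately.

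**Stopping.** Section 4.4 has two lists. The first opens "Participants should stop PrEP in the event of any of the following reasons" and names HIV infection and unacceptable toxicity or adverse event. The second opens "Participants may stop PrEP for any of the following reasons" and includes "Any change in the participant's sexual behaviour or circumstances that justifies the discontinuation of PrEP". Loss of eligibility is not named as such in either list.

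**Follow-up and supply.** At the 3-monthly visit (section 5.4.3), "The clinician should check that the participant is still eligible for PrEP and wishes to continue", and the result is coded in GUMCAD. Section 5.4.4 has a similar check at the annual visit. In both sections the next sentence allows dispensing once the standard assessments are done. Section 5.5 allows up to 3 months' supply per visit. Section 3.5 ties stopping and restarting to risk and eligibility.

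**Data.** Eligibility, offer, uptake and duration of use are coded at participant level (section 8.6). Dispensing date and quantity are recorded for each patient (section 10.6).

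**The concern.** Eligibility and PrEP use are two separate yes/no facts, and the trial is meant to estimate the duration of each. A model that splits only the eligible by use can report both durations correctly only if nobody takes PrEP while ineligible. Section 1 expects users to move in and out of periods of risk, so lapses of eligibility during a course of PrEP are foreseeable.

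Two uses of the results are at stake. Duration of PrEP use is a named input to the economic model (section 8.4), which informs NHS England on cost-effectiveness and budget impact. Section 1 also calls it essential for a future programme to be able to audit compliance with the eligibility criteria. PrEP time outside the criteria measures that directly, and the three states do not report it. If the coding of such time were left to local practice, differences in duration between clinics could also partly reflect coding.

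**Working it through.** The documents give no mean or variance for duration of use (section 8.1 says both are unknown), so there is no planned figure to reproduce. The check is a cross-tabulation, followed by simple state-time arithmetic.

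**Step 1. Map the four possible combinations to the three states.**

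| | On PrEP | Off PrEP |
|---|---|---|
| Eligible | State 1 | State 2 |
| Ineligible | State 3 | State 3 |

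The states are exhaustive, because the third label does not say that the person is off PrEP. Duration of eligibility is state 1 + state 2, with no loss. Duration of use is state 1 only, and the on-PrEP part of state 3 cannot be separated out.

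**Step 2. Is the ineligible/on cell empty by rule?** Towards empty: section 3.5 links stopping and restarting to eligibility, and sections 5.4.3 and 5.4.4 place an eligibility check just before dispensing. Against: no section requires PrEP to stop when the criteria are no longer met, section 4.4 puts the nearest reason in the permissive list, the follow-up sections state no consequence of a failed check, and up to 3 months' supply can be in hand when eligibility lapses. The cell is neither expressly allowed nor ruled out.

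**Step 3. Size, as an illustration only.** All values are assumed, for one course of PrEP:
- U = true months on PrEP: 6, 12 or 24
- g = months on PrEP while ineligible: 0, 1.5 or 3 (3 being the maximum supply between checks)
- h = months eligible and off PrEP: 3

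True duration of use is U. True duration of eligibility is U − g + h.

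*Coding A, labels as written.* Ineligible/on time goes to state 3. Use is recorded as U − g, a relative error of −g/U. Eligibility is recorded as U − g + h, with no error.

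*Coding B, anyone on PrEP coded eligible.* Use is recorded as U, with no error. Eligibility is recorded as U + h, a relative error of +g/(U − g + h).

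| U | g | A: error in use | B: error in eligibility |
|---|---|---|---|
| 6 | 1.5 | −1.5/6 = −25.0% | 1.5/7.5 = +20.0% |
| 12 | 1.5 | −1.5/12 = −12.5% | 1.5/13.5 = +11.1% |
| 24 | 1.5 | −1.5/24 = −6.2% | 1.5/25.5 = +5.9% |
| 6 | 3 | −3/6 = −50.0% | 3/6 = +50.0% |
| 12 | 3 | −3/12 = −25.0% | 3/12 = +25.0% |
| 24 | 3 | −3/24 = −12.5% | 3/24 = +12.5% |

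With g = 0 every error is zero.

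**Step 4. Splitting of courses.** Under coding A, if the lapse falls within a course rather than at its end, the course becomes two visits to state 1. With U = 12 and g = 1.5, the mean time per visit is (12 − 1.5)/2 = 5.25 months, although the person took PrEP for 12 months without a break.

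**The case against.** The strongest reply is that the protocol intends supply to depend on eligibility, so the missing cell should be close to empty. Section 3.5 and the checks before dispensing support this. The permissive list in section 4.4 also covers termination of the trial and withdrawal by the investigator, so its wording cannot be read as leave to carry on regardless. This stands in part: a reader might infer that the rules let an ineligible participant stay on PrEP, and no section grants that. It does not close the gap, because no section requires stopping either, and supply already in hand is not recalled.

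A reader might also infer that one of the two durations must be wrong. That does not follow. With the labels as written, eligibility is sound and only use is at risk, and only if such time occurs.

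A third inference is that a current user who does not "Report condomless intercourse (excluding oral) in the previous 3 months" becomes ineligible at the next visit. Section 3.3 sets that as an enrolment criterion, Table 1 marks the inclusion and exclusion criteria at baseline only, and no section says that a current user must meet it again.

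Nor would use outside the criteria be invisible. The GUMCAD codes and dispensing records could show it outside the model. Section 8.3 does not say that they will be used in this way.

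Finally, section 8.3 leaves the detailed description to the SAP, and no separate SAP text is in the document reviewed. A coding rule may exist there. Even so, the protocol itself states three states, and followed literally they leave this time out of duration of use.

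**Conclusion.** The concern holds in a limited form. The stated model merges ineligible participants on and off PrEP, and the protocol neither rules out PrEP time while ineligible nor says how to count it. Any such time is lost from duration of use, and a continuous course may be split. If users are coded eligible by default, duration of eligibility is overstated instead.

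The size cannot be derived from the documents. On the assumed values above, the understatement of use runs from zero to 50%, with 12.5% for 1.5 ineligible months in 12. These are illustrations and not estimates for this trial. This is a worthwhile, low-cost correction to a main outcome; it does not show that the duration results will be wrong.

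**What to change.** In section 8.3 item 3, and in the SAP if it repeats the three states, split the ineligible state into on PrEP and off PrEP. Take PrEP use from dispensing records and eligibility from the visit codes, each determined without reference to the other. Then report:
- duration of use as the sum of the two on-PrEP states;
- duration of eligibility as the sum of the two eligible states;
- the share of PrEP time that falls outside the criteria.

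The rule for leaving and re-entering the analysis should be worded so that a lapse of eligibility alone does not end a period of use.

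The cost is a change of wording and one more state, using data already collected. There are limits. Some transitions will be sparse; if the new state is nearly empty, report its total time descriptively instead of modelling it. Eligibility is observed only at visits, so the date of a lapse between visits stays unknown under either model. Dispensing is an imperfect marker of being on or off PrEP for event-based users; section 4.6 treats pills dispensed and days between visits only as a measure of the opportunity to adhere.

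Separately, sections 3.5, 4.4, 5.4.3 and 5.4.4 should be reconciled on what follows when eligibility lapses. Which clinical rule is right is not a matter for this review.
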